Outcome Measures	
Primary Outcome Measures :
 
 ● Overall postoperative morbidity rates 
Secondary Outcome Measures :
 
 ● Intraoperative morbidity rate ● Operative time ● Estimated blood loss ● Number of harvested and metastatic lymph nodes ● the lengths of incision, proximal and distal margins ● Time to first flatus ● Time to first liquid diet ● Postoperative hospital stay ● Total cost
Statistical considerations	
All data analyses will be performed using SPSS statistical software, version 23.0 (SPSS Inc), and the R software environment (R Foundation for Statistical Computing).
 
All data analyses will be conducted on a per-protocol (PP) basis. This study does not fill in missing values. Normally distributed continuous variables will be presented as mean and standard deviation and compared using the t-test if normally distributed, or as median and interquartile range and compared using the Wilcoxon rank-sum test if non-normally distributed; while categorical data will be presented as number and percentages and compared using the Pearson χ^2 test or the Fisher exact test, as appropriate. Sensitivity analysis is used for extreme outlier data. The confidence interval of the parameters is estimated with a 95% confidence interval. The central effect analysis and subgroup analysis are conducted according to the specific situation. All the statistical tests were tested by two sides. A p-value <0.05 is considered statistically significant.

1. Research background

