4.3 Withdraw criteria

- (16) Patients intraoperatively/postoperatively confirmed as T4b
- (17) M1 tumor confirmed intraoperatively or postoperatively: distant metastasis only found by intraoperative exploration or postoperative pathological biopsy or a positive postoperative peritoneal lavage cytology examination
- (18) Requirement of simultaneous surgery for other diseases
- (19) Patients intraoperatively confirmed as unable to complete D2 lymph node dissection/R0 resection due to tumor: unable to complete R0 resection due to regional lymph node integration into a mass or surrounded with important blood vessels, which cannot be resected
- (20) Sudden severe complications during the perioperative period (intolerable surgery or anesthesia), which renders it unsuitable or unfeasible to implement the study treatment protocol as scheduled
- (21) Patients who voluntarily quit or discontinue treatment for personal reasons at any stage after inclusion in this study
- (22) Treatment implemented is proven to violate study protocol.

5. Outcome Measures

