8.1 Incidence of operative complications

The number of all patients treated with surgery as the denominator and the number of the patients with any intraoperative and postoperative complications as the numerator are used to calculate the proportions. The criteria for the intraoperative complications refer to the descriptions of intraoperative complications in the observation project (in 9.3.3).

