8.1.1 Incidence of intraoperative complications

With the number of patients undergoing surgery as the denominator, the number of patients with any of the following intraoperative complications is calculated as numerator. Intraoperative complications are based on the intraoperative complications mentioned in the intraoperative observations.

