8.2 Mortality

- The number of all the patients receiving surgery as the denominator and the number of the patients in any of the following situations as the numerator are used to calculate proportions. This proportion indicated the operative mortality ratio.

- Situations: patients whose death was identified according to documented intraoperative observation items, including patients who die within 30 days after the surgery (including 30 days) regardless of the causality between the death and the surgery, and patients who die more than 30 days after the surgery (whose death is proved to have a direct causal relationship with the first operation).

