9.2 Preoperative management

- In case of any deterioration of the clinical conditions from the selection time to the expected day of surgery, whether to undergo an elective surgery as planned should be decided in accordance with the judgment of the doctor in charge; if an emergency surgery is required, the case should be withdrawn from PP set according to Withdrawal Criteria;
- For patients with nutritional risks, preoperative enteral/parenteral nutritional support is allowed.
- For elderly, smokers, high-risk patients with diabetes, obesity, and chronic cardiovascular/cerebrovascular or thromboembolic history, among others, perioperative low-molecular-weight heparin prophylaxis, lower-limb antithrombotic massage, active lower limb massage, training in respiratory function, and other preventive measures are recommended. For other potentially high-risk complications not specified in this study protocol, the doctor in charge can decide on the most appropriate approach according to clinical practice and should record it in the CRF.
- For the operative approach of the surgeries in this study should be selected by the doctor in charge according to his/her experience and the specific intraoperative circumstances.
- Preoperative fasting and water deprivation and other before-anesthesia requirements on patients should follow the conventional anesthesia program, which is not specified in this study.
- For prophylactic antibiotics, the first intravenous infusion should begin 30 minutes before surgery. It is recommended to select a second-generation cephalosporin (there are no provisions on specific brands in this study); the preparation, concentration, and infusion rate should comply with routine practice; and prophylaxis should not exceed postoperative 24 hours (special case can be extended to 48 hours) at a frequency of one infusion every 12 hours. If a patient is allergic to

cephalosporins (including the history of allergy or allergy after cephalosporin administration), other types of antibiotics are allowed according to the specific clinical situation and when used over the same period mentioned.

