9.3.1.10 Regulations Regarding Concurrent Surgical Treatments

If another organ/system disease is present, the responsible surgeon and the relevant department consultants will jointly decide whether a concurrent operation is required and can be performed. The order is determined according to the clinical routine, but these cases will be excluded from the PP set according to the Exclusion Criteria.

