9.3.1.11 Regulations Regarding the Processing of Excluded Patients Identified Intraoperatively

If the patient is judged to meet the exclusion requirements during the operation, the study approach will be suspended, and the responsible surgeon will decide upon the subsequent treatment according to the clinical practice of the research center (the therapeutic decision, such as whether to excise the gastric primary focus or metastases, is determined by the responsible surgeon). These cases will be excluded from the PP set according to the Exclusion Criteria.

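### The primary morbidity rate has two denominators, all operated patients (section 8) and the per-protocol set (section 10.1), and withdrawal criterion 20 may link removal to a complication

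*Protocol*

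**What the plan says.** **Denominator.** Section 8.1 of the protocol, on operative complications, uses "The number of all patients treated with surgery as the denominator", and 8.1.2 repeats this for postoperative complications. Section 8.1.1 has "With the number of patients undergoing surgery as the denominator" and section 8.2, on mortality, "The number of all the patients receiving surgery as the denominator".

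**Analysis set.** The Summary (Statistical considerations) and section 10.1 both state: "All data analyses will be conducted on a per-protocol (PP) basis". Section 10.1 also names a safety population for safety indicators and adverse reactions, but does not assign the primary outcome to it.

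**Withdrawal.** Section 4.3, criterion 20, lists: "Sudden severe complications during the perioperative period (intolerable surgery or anesthesia), which renders it unsuitable or unfeasible to implement the study treatment protocol as scheduled".

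**Route out of the PP set.** The protocol describes removal in three situations:
- emergency surgery needed before the planned operation (9.2): "the case should be withdrawn from PP set according to Withdrawal Criteria";
- concurrent surgery for another disease (9.3.1.10): "these cases will be excluded from the PP set according to the Exclusion Criteria";
- exclusion grounds found during the operation (9.3.1.11), in almost the same words as 9.3.1.10.

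The primary outcome is overall postoperative morbidity (5.1), with a 30-day window, or first discharge if the stay is longer (8.1.3). The design is open (3.4).

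**The concern.** An operated patient who is outside the PP set counts under section 8 and does not count under section 10.1. For the primary outcome these are two different rates, and the non-inferiority decision could differ between them.

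Most withdrawal grounds (T4b or M1 disease, concurrent surgery, no D2/R0 resection) are not complications. Criterion 20 is different, because its trigger is a severe complication. A patient removed under it who also has a primary event drops out of numerator and denominator together, so that arm's rate falls. In an open study, whether a case meets the criterion is a judgement made with the approach known.

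**Working it through.** **1. The texts side by side.** Take a patient whose operation was begun and who is then withdrawn under 4.3. Under 8.1 and 8.1.2 the patient is in the denominator and, with a complication, in the numerator. Under 10.1, if withdrawal means leaving the PP set, the patient is in neither. No sentence says which rule governs the primary rate.

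**2. How far criterion 20 reaches.** It requires that treatment cannot go ahead as scheduled, so it points mainly to events before or during the operation. A complication after a completed gastrectomy does not plainly meet it, and a patient never operated on is outside both denominators. There is some overlap with the primary outcome: 8.1.2 counts intraoperative as well as postoperative complications in its numerator, although 8.1.3 refers only to postoperative items. The step from criterion 20 to the PP set is an inference from 9.2.

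**3. The plan's own figure.** Section 3.3 gives 15% in both arms, a 15-point margin, alpha 0.05, power 80%, 68 per group and 75 after a 10% allowance. Exact binomial power of the unpooled Z test at one-sided 0.05 first reaches 80% at n = 68 (80.03%). The sample size therefore reproduces at one-sided 0.05, which is used below.

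**4. Effect of one patient.** With 75 in an arm:
- one event patient removed at a 15% rate: 11.25/75 − 10.25/74 = 1.15 points lower;
- one event patient removed at a 30% rate: 22.5/75 − 21.5/74 = 0.95 points lower;
- one patient without an event removed: 0.20 or 0.41 points higher.

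**5. Effect on the non-inferiority decision.** Assume true rates at the margin, p1 = 0.30 (robotic) and p2 = 0.15 (laparoscopic), with 75 operated per arm. Let w be the share of an arm withdrawn and f the share of those withdrawn who have an event. The protocol gives no value for w or f; 3-5% is about 2 to 4 patients per arm. Then

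q = (p − f·w)/(1 − w), n = 75(1 − w), SE² = q1(1 − q1)/n1 + q2(1 − q2)/n2,

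P(non-inferiority declared) = Φ((0.15 − (q1 − q2))/SE − 1.645).

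Example, robotic arm only, w = 0.05, f = 1: q1 = 0.25/0.95 = 0.263, n1 = 71.25, SE = 0.0665; (0.15 − 0.113)/0.0665 = 0.554; Φ(0.554 − 1.645) = 13.8%.

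| Loss of 3% to 5% of patients | f = 0.5 | f = 1 |
|---|---|---|
| None (reference) | 5.0% | 5.0% |
| Robotic arm only | 6.0% to 6.8% | 9.3% to 13.8% |
| Robotic 3-5%, laparoscopic 1.5-2.5% | 5.1% to 5.2% | 6.5% to 7.9% |
| Equal in both arms | 4.3% to 3.9% | 4.3% to 3.8% |
| Laparoscopic arm only | 3.5% to 2.7% | 2.0% to 1.0% |

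If robotic-only losses have events at the arm's own 30% rate, the result stays at 5.0%.

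**6. The opposite risk.** Keeping everyone operated on can dilute a true difference. If 5% or 10% of each arm (assumed) meet criteria 16-19 and have one common complication rate, 15 points become 15 × 0.95 = 14.25 or 15 × 0.90 = 13.5, and false non-inferiority rises from 5% to about 6.3% or 7.8%.

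**The case against.** The strongest reply has four parts.

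*The link is inferred.* No text removes an operated criterion 20 patient from the PP set. Section 9.2 concerns emergency surgery before the planned operation, and 9.3.1.12 answers severe intraoperative events with conversion and a recorded reason, not withdrawal. This stands. A reader might infer that the protocol already discards complicated patients from the primary rate; the documents do not say so.

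*The direction is open.* A reader might also infer a bias towards non-inferiority. That needs the robotic arm to lose more event patients. Equal losses, or losses in the laparoscopic arm, make the test conservative. This stands too.

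*PP is a recognised choice for non-inferiority.* It is, because it avoids dilution, and the dilution in step 6 is of similar size to the bias in several rows of the table. This argues against resting the decision on the all-operated set alone. It does not argue for leaving the denominator unsettled.

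*The texts can be read together.* Section 8 could mean operated patients within the analysed set, or the safety population could cover complications, and section 10.1 refers to a separate statistical analysis plan for more detail. But section 8 speaks of all operated patients, the safety population is not tied to the primary outcome, and the same list makes all analyses PP. A more detailed plan would inherit two conflicting instructions from the protocol.

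**Conclusion.** The denominator conflict is in the text and should be fixed. Its existence rests on no assumed figure: sections 8.1 to 8.2 and section 10.1 give different rates as soon as one operated patient is withdrawn and left out of the PP set.

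The criterion 20 bias is conditional. It requires that the criterion removes patients from the PP set, that they were operated on, and that they had events counted in the primary rate. The group is probably small. Across the one-arm and equal-loss scenarios with 3-5% loss, false non-inferiority ranges from 1.0% to 13.8% against a nominal 5%. The upper end needs losses in the robotic arm only, with an event in every patient lost. These figures show what could happen and are not an estimate for this trial.

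**What to change.** Reconcile sections 4.3, 8.1 and 10.1:

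- State in 10.1 that the primary morbidity rate is computed over all patients treated with surgery, which is the 8.1 denominator.
- State that an operated patient who meets criterion 20 stays in the denominator, with complications in the 8.1.3 window counted as events, in both the all-operated and the PP analysis. This concerns counting only and leaves the clinical handling of such patients as it is.
- Report the PP analysis, which may still leave out criteria 16-19 cases, beside the all-operated one. Claim non-inferiority only if both support it, because the all-operated set can dilute a true difference and the PP set can be selective.
- Report by arm the number withdrawn under each criterion.

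The cost is wording in three sections, one extra analysis and a slightly stricter conclusion. Complications are already recorded (9.3.2, 9.3.4) and 30-day follow-up covers all patients (9.4.1). Recording the intended approach, the handling of conversions and missing 30-day outcomes are separate points.

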9.4 Follow-Up

9.4.1 Follow-up Period and strategy

Follow-up visits will be completed by special persons for all cases selected in this study .All patients are followed up with 30 days, Recommend patient follow-up every 3 months during the first 2 years and then every 6 months beyond the third year (1、 3、 6、 9、 12、 15、 18、 21、 24、 30 and 36 months after the operation),and record with patients’ consent. This study suggests that the above examinations should be conducted in the patient's primary surgical research center, but does not exclude outer court review. For Outer Court review, It recommended that visiting the hospital as a three-level hospital, and these information will be recorded by the follow-up specialist. The occurrence of tumor recurrence or metastasis and the survival status of all patients are evaluated and recorded according to the results of the various examinations. Patients who refuse to follow the protocol should be recorded as lost to follow-up, and at the end of the study, these cases should be analyzed together with cases lost to follow-up in line with the criteria of this study.

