9.5 Post-operative adjuvant therapy

9.5.1 Indications for postoperative adjuvant chemotherapy

After completion of the surgical treatment, according to the postoperative pathological results, subjects among the R0 resection cases that are stage II and above are administered postoperative adjuvant chemotherapy according to the provisions of this program.

For cases of non-R0 resection or recurrence after R0 resection, this study does not

stipulate the follow-up treatment plan; the research center decides on the action to be taken according to the clinical treatment routine.

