9.5.2 Postoperative adjuvant chemotherapy

This study uses a combination of chemotherapy based on 5-FU (5-fluorouracil) and recommends the SOX regimen.

In cases of good physical and tolerable conditions, chemotherapy is first started within 3-4 weeks after surgery and then according to the regularity of the chemotherapy cycle.

During the chemotherapy period, tumor recurrence should be assessed according to the follow-up plan.

When tumor recurrence occurs during chemotherapy, the adjuvant chemotherapy regimen of this study is discontinued. The follow-up treatment is decided by the research center according to the clinical treatment routine. This study does not make regulations, but the cause and follow-up treatment plan should be recorded in the CRF.

Adjuvant chemotherapy requires written approval from the patient.

Subjects that refuse postoperative adjuvant chemotherapy or do not complete the adjuvant chemotherapy are not excluded from this study, but the cause is marked and recorded in the CRF.

Patients who choose adjuvant chemotherapy, irregular chemotherapy, or a non-first-line regimen are not excluded from the study, but Safety Evaluation Committee is obliged to monitor patient safety during follow-up. The patient's chemotherapy medication must be recorded in the CRF.

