10.1 Statistical analysis plan

- Statistical software: we will use SPSS statistical software, version 23.0 (SPSS Inc), and the R software environment (R Foundation for Statistical Computing) to perform statistical analyses.
- Basic principle: The method of differential testing was adopted. The safety population of the study consists of the patients who receive safety evaluation data after the intervention. Descriptive statistics and two-sided tests were conducted for the safety indicators and the incidence of adverse reactions. A p-value <0.05 is considered statistically significant. The confidence interval of the parameters is estimated with a 95% confidence interval.
- Shedding analysis: Total shedding rate of two groups and loss rate due to adverse events will be compared using pearson χ^2 test

- All data analyses will be conducted on a per-protocol (PP) basis.
- Method of outlier determination: the observation value is greater than P75 or less than P25, and the exceed value more than 3 times of the quartile spacing ($=p75-p25$), which will be sentenced to outlier data. During the analysis, the sensitivity analysis is used for outlier data, namely analyzing outcomes including or excluding outlier's data. and if the results are not contradictory, the data is retained; if the contradiction, it depends on the specific circumstances.
- Descriptive statistics: The measurement data gives the mean, the standard deviation and the confidence interval, and the minimum value, the maximum value, the P25, the median and the P75 are given when necessary; matched data also gives the mean and standard deviation of the gap-value, and the median and average rank of the Non-parametric method. The nominal-scale data gives the frequency distribution and the corresponding percentages. The level data gives the frequency distribution and the corresponding percentages, as well as the median and the average rank. Qualitative data give positive rate, positive number, and denominator numbers. The survival data gives the number of events, the number of deletions, the median survival time, and the survival rate.
- Subgroup analysis : Sub-group analysis is to find the factors that may affect prognostic according to the specific circumstances of the data.
- Missing values handling: This study does not fill in missing values

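### Criterion 21 in section 4.3, read literally, lets behaviour after surgery remove operated patients from the 30-day morbidity analysis, in conflict with sections 8.1.2 and 9.5.2

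*Protocol*

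**What the plan says.** All references are to the protocol.

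- **Section 4.3 (21)** lists among the withdrawal criteria "Patients who voluntarily quit or discontinue treatment for personal reasons at any stage after inclusion in this study". The word treatment is not limited to the operation. Criterion 22 adds: "Treatment implemented is proven to violate study protocol".
- **Section 9.2** shows what withdrawal does to the analysis. For a patient who comes to need emergency surgery, "the case should be withdrawn from PP set according to Withdrawal Criteria".
- **Section 10.1**: "All data analyses will be conducted on a per-protocol (PP) basis". The summary table repeats this. Section 10.1 also names a safety population: "The safety population of the study consists of the patients who receive safety evaluation data after the intervention".
- **Section 9.5.1** makes chemotherapy part of the study programme. R0 patients at stage II and above are "administered postoperative adjuvant chemotherapy according to the provisions of this program".
- **Section 9.5.2**: "Subjects that refuse postoperative adjuvant chemotherapy or do not complete the adjuvant chemotherapy are not excluded from this study". It treats irregular or non-first-line chemotherapy in the same way. It does not mention the PP set.
- **Section 8.1.2** takes every patient who had surgery as the denominator for postoperative complications. Section 8.1.3 closes the window at day 30, or at first discharge if the stay is longer.

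**The concern.** Take a patient who has the study operation, is observed to day 30, and later stops chemotherapy for personal reasons. Criterion 21 withdraws this patient, and the PP rule then removes the patient from the primary analysis. Section 9.5.2 keeps the patient in the study, and section 8.1.2 keeps the patient in the denominator. The protocol does not say which text prevails, so both sections 4.3 and 9.5.2 can be honoured by keeping the patient in the study but dropping the patient from the PP set.

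The primary outcome is 30-day morbidity. If membership of the analysis set depends on what the patient does after surgery, it can depend on the outcome itself. Should patients with a complication leave more often, complications are removed preferentially, observed rates fall in both arms, and a true excess in the robotic arm is compressed. In a non-inferiority comparison that favours the conclusion sought. The study is open and non-randomised, so the choice between the two readings could also be made by people who know group and outcome.

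**Working it through.** **1. The texts applied to one patient** (operated, then stops chemotherapy for personal reasons)

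| Section | Consequence |
|---|---|
| 4.3 (21) with 9.2 and 10.1 | Withdrawn, hence out of the PP set and the primary analysis |
| 9.5.2 | Not excluded from the study; PP membership not stated |
| 8.1.2 | Counted in the denominator |

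**2. Timing.** Section 9.5.2 starts chemotherapy 3-4 weeks after surgery, about days 21-28. The usual window closes at day 30. The decision to start can therefore fall 2-9 days before the window closes; completion falls after it.

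**3. The plan's own sample size (section 3.3).** Inputs: 15% in both arms, margin 15% taken as 15 percentage points, alpha 0.05, power 80%. The sample-size text does not state sidedness. Exact binomial enumeration of the unpooled Z test at one-sided 5% first reaches 80% power at n = 68 per group (0.8003), the stated figure. For dropout, 68 x 1.1 = 74.8, so 75, as stated.

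**4. Illustration of the bias.** Assumed, not from the documents: a share r0 of patients without a complication leave the set, and r1 = 2 x r0 of those with one, the same in both arms. With true rate p:

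- retained share: s = p(1 - r1) + (1 - p)(1 - r0)
- apparent rate: p(1 - r1) / s

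*r0 = 0.15, r1 = 0.30*
- p = 0.30: s = 0.30 x 0.70 + 0.70 x 0.85 = 0.805; apparent rate 0.210 / 0.805 = 26.1%
- p = 0.15: s = 0.15 x 0.70 + 0.85 x 0.85 = 0.8275; apparent rate 0.105 / 0.8275 = 12.7%
- apparent difference: 13.4 points

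*r0 = 0.20, r1 = 0.40*
- p = 0.30: s = 0.30 x 0.60 + 0.70 x 0.80 = 0.740; apparent rate 0.180 / 0.740 = 24.3%
- p = 0.15: s = 0.15 x 0.60 + 0.85 x 0.80 = 0.770; apparent rate 0.090 / 0.770 = 11.7%
- apparent difference: 12.6 points

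A true 30% against 15% lies exactly on the margin, so declaring non-inferiority there is an error. The same exact test, with 75 operated per arm and the retained numbers rounded, gives:

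| Scenario | Retained (robotic / laparoscopic) | Chance of false non-inferiority |
|---|---|---|
| Nobody removed | 75 / 75 | 5.2% |
| r0 = 0.15, r1 = 0.30 | 60 / 62 | 8.4% |
| r0 = 0.20, r1 = 0.40 | 56 / 58 | 10.4% |

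If r1 = r0, the formula returns p and there is no bias. The effect rests wholly on leaving being related to complications.

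**5. Equal arms and power.** With true rates of 15% in both arms, the same removal gives 12.7% against 12.7%, or 11.7% against 11.7%. The difference stays zero. Exact power at those rates is 81.4% (n = 62) and 81.5% (n = 58), against 80.0% at n = 68 and 15%. There is no power loss to report.

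**The case against.** The strongest reply is that section 9.5.2 is the only text on chemotherapy non-adherence, and it says that such patients are not excluded. On ordinary reading a specific rule governs a general one, so criterion 21 would not reach them. Nor would criterion 22, since conduct that 9.5.2 allows does not violate the protocol. This is probably the intent, and it lowers the weight of the point. It does not close it: precedence is stated nowhere, criterion 21 expressly covers any stage after inclusion, and remaining in the study is not the same as remaining in the PP set.

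The mechanism is also narrower than it looks. Criterion 21 concerns personal reasons, whereas a complication would often prevent chemotherapy for medical reasons. Section 9.5.2 starts chemotherapy only in patients fit for it, and section 9.5.1 only in R0 cases at stage II and above. The illustration applies its leaving rates to all 75 per arm and may therefore overstate the effect. This stands.

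Four stronger readings are tempting, and the document does not support them:

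- *A third, contradictory fate.* Section 9.4.1 says "Patients who refuse to follow the protocol should be recorded as lost to follow-up". It concerns follow-up visits and how non-attenders are recorded. It conflicts with the other rules only if stretched to cover treatment.
- *No other population exists.* Section 10.1 names a safety population, and section 8.1.2 uses an all-operated denominator.
- *Adherence is settled wholly after the endpoint.* Chemotherapy may start inside the 30-day window; only completion clearly follows it.
- *Lost power, or bias when the arms are equal.* Step 5 of the working shows neither under these assumptions.

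**Conclusion.** The point holds as a conflict of wording that reaches the primary analysis: section 4.3 (21), through 9.2 and 10.1, can remove operated patients whom 8.1.2 counts and 9.5.2 keeps in the study. The conflicting rules are all in the protocol, so this is not a detail left to a statistical analysis plan.

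The direction of harm is toward declaring non-inferiority, provided that leaving is more common after a complication. Its size cannot be derived from the document. Under the assumed rates, a 15-point difference appears as about 13.4 or 12.6 points, and the error rate rises from about 5% to 8-10%. These figures also assume a one-sided 5% test and equal leaving behaviour in both arms; they are illustrations, not estimates. The passages should be reconciled, although the authors probably intended the reading in 9.5.2.

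**What to change.** Reconcile section 4.3 (21) and (22) with 8.1.2 and 9.5.2:

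1. In 4.3, state that, for analysis-set membership, criteria 21 and 22 apply only to events up to completion of the study operation.
2. In 4.3 and 10.1, state that later non-adherence to adjuvant chemotherapy or to follow-up visits does not remove an operated patient from the 30-day morbidity analysis.
3. State that complications recorded up to last contact are kept, and add a cross-reference in 9.4.1 so that a lost-to-follow-up record does not delete them.

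The change concerns the analysis set only and alters no treatment rule. It costs a few sentences and needs no further patients or data.
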